4.1. Non-compartmental pharmacokinetic analysis

Non-compartmental analysis (NCA) will be performed as described previously.¹ The NCA PK parameters will be calculated for each subject and study period using the formulas implemented in the Phoenix / WinNonlin Professional software. Whenever possible, at least three observations above the quantification limit will be used to estimate the terminal slope. The ANOVA statistics will be calculated for Cmax, AUC_{0-last}, and AUC_{0-inf}. Descriptive statistics will be calculated and reported for all PK parameters.

The NCA PK parameters will be calculated and NCA PK results sent to the FDA colleagues **before unblinding**. Summary statistics will be calculated after subsequent unblinding.

4.2. Statistical analysis to address objective I

For bioequivalence statistics, the formulation with the larger MMAD will be treated as the reference formulation in each pairwise comparison (**Table 2**).

Table 2: Pairwise comparisons while treating the replicates of formulation 15-mm-015 separately

Comparison	Test formulation	Reference formulation
1	15-mm-016	15-mm-017
2	15-mm-015 (3a)	15-mm-017
3	15-mm-015 (3b)	15-mm-017
4	15-mm-015 (3a)	15-mm-016
5	15-mm-015 (3b)	15-mm-016
6	15-mm-015 (3a)	15-mm-015 (3b)

Bioequivalence statistics: Following the FDA guidelines ², ANOVA statistics will be performed based on ln-transformed data. For each comparison, the ratio of geometric means and the 90% confidence interval for this ratio will be calculated. We will include effects for treatment, period, sequence and subject within sequence in the ANOVA. Equivalence statistics will be performed using the equations implemented in Phoenix / WinNonlin Professional or SAS.

Reference

2. Food and Drug Administration; Center for Drug Evaluation and Research (CDER). Guidance for Industry Statistical Approaches to Establishing Bioequivalence. *FDA Guideline* 2001: 1-48.

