## Methodology (Design)

This is a single center, double-blind, single-dose (500 mcg), randomized, four period, four sequence cross over PK study to evaluate the local (lung) bioequivalence (**BE**) of 100 mcg fluticasone propionate formulation 1(**FPF I**), 100 mcg fluticasone propionate formulation 2(**FPF II**) and 100 mcg fluticasone propionate formulation 3 (**FPF III**). FPF III will be replicated in the study to provide an assessment of bioequivalence when FPF III is tested against itself.

During the screening visit, the inclusion and exclusion criteria will be reviewed to ensure the subject is appropriate for the study. The informed consent will be reviewed with the subject by a member of the study team and the subject will be encouraged to ask questions to ensure the subject has a good understanding of the study. If the subject is eligible and agrees to participate, the subject will be asked to sign the informed consent form prior to any study specific procedures. After their consent, demographic data, medical history and concomitant medications will be recorded. A physical examination will be performed after the vital sign measurements are obtained. A pregnancy test for female subjects must be negative (test repeated if the subject continues in the study for more than 30 days). Spirometry testing and inhalation training will be performed to ensure the suitability of subjects. Laboratory tests such as Complete Blood Count with differential, urinalysis and basic metabolic panel will be performed. Screening tests will be performed within 28 days of study visit 1 and no later than 2 days before study visit 1. All screening results will be evaluated by the study clinician/investigator against the inclusion/exclusion criteria to confirm the eligibility of the subjects.

A minimum period of 5 days should lapse between the subsequent study visits. At each study visit, review of the eligibility criteria, documentation of any changes in medical history including concomitant medications, vital signs, inhalation training, insertion of the indwelling catheter into the forearm region of the subject for blood collection, administration of the formulation by inhalation, blood sampling as per protocol will be performed. The total duration of the study is estimated to be approximately 10 weeks.

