### 3. Study Design

The study comprises of 5 visits: 1 screening visit and 4 study visits.

On each study visit day, subjects will get 5 inhalations from one of the following formulations:

Study Drug	Device	Formulation
1	Plastiape Monodose DPI	Fluticasone Propionate Formulation 1 (FPF I)
2	Plastiape Monodose DPI	Fluticasone Propionate Formulation 2 (FPF II)
3	Plastiape Monodose DPI	Fluticasone Propionate Formulation 3 (FPF III)

The following sequences will be used in the study:

Sequence	Study Visit 1	Study Visit 2	Study Visit 3	Study Visit 4
1	FPF I	FPF II	FPF III	FPF III*
2	FPF II	FPF III*	FPF I	FPF III
3	FPF III	FPF I	FPF III*	FPF II
4	FPF III*	FPF III	FPF II	FPF I

Note that in this design every study drug appears once in each period. Also every study drug is immediately followed only once by each of the other study drugs.

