# **7. Statistical Methods and Analysis of Data**

## **7.1 Sample Size Calculation**

Using in-house and literature PK data for fluticasone propionate, the variability in the PK parameters  $C_{max}$  and  $t_{max}$  were estimated to be between 20% to 40% (%CV). If the %CV is 30% and the products differ by only 5%, a sample size of 40 (no dropouts) was initially thought to be appropriated to have 80% power to show that the products are equivalent.

$$N = 2(t_{\alpha,2N-2} + t_{\beta,2N-2})^2 * [CV/(V - \delta)]^2$$

N = total number of subjects required to be in the study

t = the appropriate value from the t distribution

$\alpha$  = the significant level

1- $\beta$  = the power, usually 80%

CV = the coefficient of variation

V = the bioequivalence limit ( $\ln 1.25 = 0.223$ )

$\delta$  = the difference between the products (for 5% difference, delta equals ( $\ln(1.05) = 0.0488$ )

However, due to budgetary constraints, the sample size was re-assessed and it was determined that the minimum number of subjects necessary to complete the study is approximately 22 subjects (considering 10% dropout rate, 24 subjects will be recruited). This sample size number does not affect the study design, which is kept as a four-way crossover (i.e., no study drug was removed from the study), and is sufficient to be utilized to achieve 80% power to show that the products are equivalent, as shown in the table below.

Case	Test / Reference Ratio (point estimator)	Intra-Individual Variability (ANOVA-CV)	Power	Sample Size (without dropouts)	Dropout Rate	Final Sample Size
1	0.95	30%	80%	40	~10%	44 (previous sample size)
2	0.95	21%	80%	22	~10%	24 subjects
3	1.00	24%	80%	22	~10%	24 subjects
4	1.05	22%	80%	22	~10%	24 subjects

**Safety Population:** All subjects randomized who received at least one dose of study drugs.

**Study Population to be Analyzed:** Analyses and summaries of pharmacokinetic data will be based on subjects who are administered all doses, complete at least 75% of blood sampling and follow the protocol procedures.

**Data Analysis:** Once the bioanalytical data is available, the pharmacokinetic data analysis will be conducted under blinded conditions. Afterwards, formulation-based analysis will be conducted under unblinded conditions.

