## 7.2 *Non-Compartmental Analysis (NCA)*

Hypothesis of the proposed research is that the three test formulations (differing in the c/p ratio) will differ in AUC and Cmax estimates. Three multiple comparisons will be performed i.e. Reference against the reference, reference against test 1 and reference against test 2. A multiplicity adjustment (e.g. bonferroni type) will be made for the 3 multiple comparisons. No additional adjustment will be made for the use of multiple metrics. NCA will be performed in WinNonlin using an inbuilt extra-vascular PK model. Standard PK metrics such as  $AUC_{(0-30min)}$ ,  $AUC_{(0-t)}$ ,  $AUC_{(0-inf)}$ ,  $C_{max}$ ,  $t_{max}$ , terminal slope/half-life,  $CL/F$ ,  $Vdss/F$ ,  $AUMC_{(0-t)}$ ,  $AUMC_{(0-inf)}$ , and MRT will be calculated for each individual plasma-concentration-time profile. ANOVA model will be used to construct univariate 90% confidence intervals for  $AUC_{(0-t)}$  and  $C_{max}$  ratios and applied to conventional 0.8 – 1.25 average BE limits. If needed, alternative BE evaluation methodology and or BE criteria may be investigated. Data will also be assessed by ANOVA methods (SAS 9.2 or another equally suitable software package) to test for statistical differences ( $p<0.05$ ).

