Data analysis plan

Pharmacokinetic Comparison of Locally Acting Orally Inhaled Drug Products ('DPI study', FDA BAA-16-00122)

1. Purpose

This document describes the non-compartmental data analysis plan for the above mentioned clinical trial. This clinical pharmacokinetic (PK) study assessed three fluticasone propionate DPI formulations (formulation 1, 2, 3) which have been characterized through *in vitro* methods. These formulations were compared in the present double-blind, randomized 4-way cross-over study; one formulation was repeated to evaluate intra-subject variability; this replicated formulation is named 3a and 3b.

2. Objectives

The primary aim of this research study is to aid the FDA in finding methods to ensure that the versions of generic drugs that are inhaled (for example, drugs used to treat asthma) are bioequivalent to the trade name drug. As a part of the research study, pharmacokinetic (PK) studies (studies measuring drug levels in the blood over time after inhalation) will be done using three different versions of fluticasone propionate (FP, a drug routinely used in asthmatic patients) administered using a dry powder inhaler (DPI, an inhalation device that delivers the drug as a dry powder).

3. Available *in vitro* data and proposed normalization

We will use the formulation with the largest Median Mass Aerodynamic Diameter (MMAD) as reference (**Table 1**).

Table 1: Summary of FPD data averaged over the 12 and 20 month time points

Formulation	FPD (<5 µm) (µg)	FPD (<3 µm) (µg)	MMAD (µm)
15-mm-016	18.707	9.977	3.77
15-mm-017	12.230	5.274	4.53
15-mm-015	15.869	8.599	3.73

We expect that the c/p ratio is determined by the MMAD with larger particles being deposited more centrally compared to smaller particles.

We will use three approaches of normalizing the PK parameters:

- 1) Normalization based on the ex-throat data
- 2) Normalization based on fine particle dose (FPD <3 µm) data
- 3) Normalization based on fine particle dose (FPD <5 µm) data

Normalization factors for the ex-throat data will be calculated separately for the VCU, AIT and OPC throats. The average normalization factors over the three throats will be used for the normalization using this approach. The normalization factors from this ex-throat approach will be used for the **primary analysis**.

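### SAP Table 2 tests the two doses of formulation 3 separately, with no pooled comparison and no rule for opposite verdicts

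*SAP*

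**What the plan says.** - SAP section 1 makes clear that 3a and 3b are one product: "one formulation was repeated to evaluate intra-subject variability; this replicated formulation is named 3a and 3b".
- The sequence table in Protocol section 3 gives both doses of FPF III in all four sequences. It adds: "Note that in this design every study drug appears once in each period".
- The PK analysis set in Protocol 7.1 requires complete dosing: "Analyses and summaries of pharmacokinetic data will be based on subjects who are administered all doses". Every analysed subject therefore has both formulation-3 doses.
- SAP 4.2 lists six comparisons under the caption "Table 2: Pairwise comparisons while treating the replicates of formulation 15-mm-015 separately". Formulation 3 meets 017 twice (rows 2 and 3) and 016 twice (rows 4 and 5). Row 1 is 016 against 017 and row 6 is 3a against 3b. For each row, "the ratio of geometric means and the 90% confidence interval for this ratio will be calculated".
- Protocol 7.2 plans fewer comparisons: "Three multiple comparisons will be performed i.e. Reference against the reference, reference against test 1 and reference against test 2". It calls for a Bonferroni-type adjustment but does not say how the replicate enters.
- The synopsis gives the replicate's purpose: "FPF III will be replicated in the study to provide an assessment of bioequivalence when FPF III is tested against itself".

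Neither document has a row for formulation 3 as a single product, or a rule for a 3a verdict that differs from the 3b verdict.

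**The concern.** The study asks whether PK can tell these formulations apart. For the two pairs that involve formulation 3, the plan produces two answers to the same question. If 3a falls inside 0.80–1.25 against 016 and 3b does not, the documents do not say whether 015 and 016 were distinguished. SAP 4.1 places summary statistics after unblinding, so the choice would be made with the results in view.

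The plan also leaves precision unused. Each formulation-3 point estimate draws on only one of the two formulation-3 doses each subject received.

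**Working it through.** **Inputs.** From Protocol 7.1: 22 completers; cases 2, 3 and 4 with (ratio, CV) of (0.95, 21%), (1.00, 24%) and (1.05, 22%); case 1 with (0.95, 30%) and 40 subjects; a CV range of 20–40%. From Protocol 7.2: limits 0.80–1.25 and 90% CIs, that is, two one-sided 5% tests. From SAP 4.2: ln-scale ANOVA with treatment, period, sequence and subject within sequence. Within-subject SD on the ln scale: s = √ln(1 + CV²).

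**1. The plan's own sample size.** With contrast variance 2s²/N and N − 2 df, the smallest even N for 80% power is 22 in cases 2, 3 and 4 (power 83.7%, 83.1%, 81.3%) and 40 in case 1 (81.6%). This matches the protocol table, which is therefore sized for one unpooled pair.

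**2. Variance of the contrasts.**
- Single: ln(3a) − ln(ref) has variance s²(1 + 1) = 2s² per subject.
- Pooled: D = ½[ln(3a) + ln(3b)] − ln(ref) has variance s²(¼ + ¼ + 1) = 1.5s² per subject.
- The SE ratio is √(1.5/2) = 0.866, about 13% smaller.

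Least squares on the actual four-sequence design agrees: 0.0911s² against 0.0684s² at N = 22 (sequences of 6, 6, 5 and 5), and 0.0833s² against 0.0625s² at N = 24.

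Example at CV 24%: s = √ln(1.0576) = 0.2366. The single CI half-width is 1.671 × 0.2366 × √(2/22) = 0.119 (60 df). The pooled half-width is 1.734 × 0.2366 × √(1.5/22) = 0.107 (18 df). The pooled interval is about 10% narrower even after the loss of degrees of freedom.

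**3. Power and disagreement at N = 22** (simulation of the actual design; pooled analysis uses per-subject D with 18 df):

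| Ratio, CV | Single | Pooled | 3a and 3b verdicts differ |
|---|---|---|---|
| 0.95, 21% | 85% | 92% | 18–19% |
| 1.00, 24% | 85% | 93% | 21% |
| 1.05, 22% | 83% | 90% | 20–21% |
| 0.95, 30% | 53% | 66% | 39% |

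Over ratios 0.95–1.05 and CVs 21–30%, disagreement runs from 10% to 40%.

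**4. What an unstated rule would imply** (CV 24%):

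| Rule | False equivalence at true ratio 0.80 | Power at ratio 1.00 |
|---|---|---|
| One comparison alone | 5% | 85% |
| Either replicate passes | 9% | 96% |
| Both must pass | 1.3% | 75% |
| Pooled D | 5% | 93% |

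**5. Dependence on the true ratio.** The primary ex-throat factors are not given. As an illustration only, take the raw ratios from SAP "Table 1: Summary of FPD data averaged over the 12 and 20 month time points". For 015/016 they are 15.869/18.707 = 0.85 and 8.599/9.977 = 0.86, with disagreement of 19–29% over CV 21–30%. For 015/017 they are 15.869/12.230 = 1.30 (disagreement 2–3%) and 8.599/5.274 = 1.63 (0%).

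**6. Subject-by-formulation interaction.** The documents do not quantify it. With assumed SDs of 0.10, 0.15 and 0.20 per formulation (CV 24%, ratio 1.00), power goes from 78% single to 86% pooled, from 68% to 75%, and from 56% to 59%. The per-subject interval keeps about 90% coverage. A pooled contrast inside the SAP's fixed-effects ANOVA falls to 88.7%, 87.3% and 86.5%.

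**The case against.** **The replicate has another purpose.** It is there for self-equivalence and intra-subject variability, row 6 serves both, and the caption suggests that separate treatment was deliberate. This is true, and it is why row 6 should stay. It does not explain why one product is tested twice against the same reference without saying which result counts.

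**The documents state no combination rule.** The error rates in step 4 therefore describe rules the plan does not contain, and a 3a/3b difference would be visible as reproducibility information. That is fair: those rates show what the open choice could cost, not what the plan commits to. The open choice is the problem.

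**Multiplicity.** Protocol 7.2 mentions a Bonferroni-type adjustment, and whether it applies to the 90% CIs is unclear. At one-sided 0.05/3, the either-passes error falls to about 3%. But single-comparison power drops to about 65–70% in the three 22-subject cases and disagreement rises to about 30–37%. Pooling still helps: 65% to 78% at CV 24%, ratio 1.00.

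**The estimator.** A pooled contrast inside the stated ANOVA keeps 60 df and has slightly more power without interaction (93%, 94%, 92% and 69% in the four cases of step 3). The price is under-coverage if interaction exists. The single comparisons also under-cover then, though less (about 89%), so the power gains in step 6 set a slightly liberal interval against a calibrated one.

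**Scope.** Pooling does not rank the three metrics or the three normalizations.

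**Conclusion.** The concern holds as a worthwhile improvement, not as an error in the listed analyses. Each row of Table 2 is valid, and the sample size reproduces. What is missing is a comparison that treats formulation 3 as the single product it is, and a rule for opposite replicate verdicts. Opposite verdicts would arise in roughly one trial in five under the protocol's own 22-subject cases, and in about two in five at CV 30%, ratio 0.95.

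Pooling cuts the standard error by about 13% and adds 7 to 8 percentage points of power in those three cases (13 points at CV 30%), with one-sided error held at 5%. This rests on equal within-subject variances and no interaction; with interaction the gain shrinks. The true normalized ratio is unknown. If the raw FPD ratios were any guide, the gap would matter mainly for 015 against 016 and hardly at all for 015 against 017.

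**What to change.** In SAP 4.2, before unblinding:

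1. Make pooled 015 against 017 and pooled 015 against 016 the deciding comparisons. For each subject compute D = mean of ln(3a) and ln(3b), minus ln(reference). Average D within each sequence, then average the four sequence means with equal weight. Build the 90% CI from the within-sequence variance of D, with N − 4 df. Equal sequence weights remove period effects because each study drug occurs once in every period. A mixed model with a subject-by-formulation term is an alternative.
2. Keep comparison 1 (016 against 017), and keep comparison 6 (3a against 3b) as the self-equivalence and within-subject CV check.
3. Report comparisons 2 to 5 as supportive and state that they do not change the verdict.
4. Reconcile the resulting four comparisons with the three comparisons and the multiplicity adjustment in Protocol 7.2.

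The cost is SAP wording and a short extra analysis step. No new data are needed, and no subject is lost, because the PK set already requires all doses. The downside is 18 residual degrees of freedom instead of 60 at N = 22, which the pooled power figures in the working already include.
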